### Study protocol

A list of patients who had gone through trauma splenectomy or bowel resection due to bowel obstruction in our center between July 2008 and July 2013, was made. Patients were divided into two groups: trauma splenectomy (exposed group) and bowel resection (unexposed group).

All patients were followed up for 5-10 years.

Our study criteria was as follows:

Exclusion criteria:

1. Disturbed lipid profile at the time of surgery, 2. Disturbed blood glucose levels at the time of surgery, 3. History of high blood pressure prior to surgery, 4. Use of any hyperglycemic agent during the follow up period, 5.  $BMI \geq 25$  at the time of surgery, 6. History of diseases potentially affecting blood glucose, e.g. hyperthyroidism, Cushing syndrome, 7. Accidental pancreatic damage during surgery, 8. Resection of  $>10$  cm of small bowel and 9. History of malignancy or radiotherapy (criteria 8 and 9 were specific to unexposed group).

Patients were contacted through phone calls. Of the 243 splenectomized patients, 90 patients who met our study criteria were willing to participate. Of 152 patients with bowel resection, 64 were willing to participate. Records of patients at the time of surgery were retrieved from hospital archive of patients' records. Patients were invited to an office meeting for assessment of blood pressure, BMI and a general physical examination and history taking. An appointment was made for drawing blood samples for measurement of lipid profile, Hb A1C and fasting blood sugar.

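### Criterion 8 caps small-bowel loss in the unexposed group but not colon loss, so non-malignant, non-irradiated colon resections of any length stay in the comparator

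*Protocol*

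**What the plan says.** All of this is in the protocol; the first three items are from the section headed Study protocol.

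- **Comparator.** The source list includes "bowel resection due to bowel obstruction in our center between July 2008 and July 2013", and the groups are labelled "trauma splenectomy (exposed group) and bowel resection (unexposed group". Neither phrase restricts the bowel segment.
- **Limit on bowel loss.** Exclusion criterion 8 concerns removal of more than 10 "cm of small bowel and 9. History of malignancy or radiotherapy (criteria 8 and 9 were specific to unexposed group". The length limit names small bowel only. Criterion 9 removes patients with past malignancy or radiotherapy. No criterion mentions colon, and no reason is given for the 10 cm limit.
- **Numbers.** The exposed count is given as "Of the 243 splenectomized patients, 90 patients who met our study criteria were willing to participate". For the comparator the protocol has "Of 152 patients with bowel resection, 64 were willing to participate". The 64 are not broken down by segment or length removed.
- **Analysis.** The Statistical analysis section compares the means of the measured variables between the two groups by Student's t-test, with significance at P below 0.05. It names no adjustment or stratification. The blood measurements are lipids, HbA1c and fasting glucose.

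**The concern.** Most of the exclusion list removes reasons other than splenectomy for abnormal glucose or lipids: disturbed values at surgery, diseases acting on glucose, pancreatic injury, drugs. Criterion 8 sits in that list and applies only to the comparator. Its natural reading is that the comparator's own operation should not disturb the outcomes. That purpose is inferred, since the protocol does not state it. On this reading the safeguard covers one part of the bowel and leaves the other open: a control with a long benign colon resection, alone or with up to 10 cm of small bowel, is eligible.

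What is at stake is attribution. Every splenectomy result is a difference from this group. If colon loss moves an outcome, the comparator mean moves, and the difference moves by the same amount in the opposite direction. A test of two group means cannot separate that from an effect of splenectomy. The shift could create an apparent effect or hide a real one, and it need not have the same direction for every outcome.

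**Working it through.** The protocol states no power, effect size or bias figure, so there is nothing of its own to reproduce. The check has a textual part and an illustrative part.

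**Text.** Three conditions together settle eligibility:
1. Entry to the unexposed group: resection for obstruction, any segment.
2. Criterion 8: out if more than 10 cm of small bowel was removed.
3. Criterion 9: out if there is a history of malignancy or radiotherapy.

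A control with a benign, non-irradiated colon resection of any length and 0 to 10 cm of small bowel removed passes all three. The gap is therefore real as written. How many of the 64 fall into it is unknown.

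**Inputs for the illustration.** From the protocol: 90 exposed, 64 unexposed, significance level 0.05 (taken as two-sided, which is not stated). Assumed, because the protocol gives neither: the share *f* of the 64 with colon resection, and the effect *s* of colon loss on an outcome in SD units, including *s* = 0.

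**Formulas.**
- Standard error of the difference: √(1/90 + 1/64) = 0.1635 SD.
- Shift of the comparator mean: *b* = *f* × *s*.
- Two-sided rejection rate with no splenectomy effect (normal approximation): Φ(*b*/0.1635 − 1.96) + Φ(−*b*/0.1635 − 1.96).

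**By size of shift.**
- *b* = 0: 5%.
- *b* = 0.10 SD: 0.10/0.1635 = 0.61; Φ(−1.35) + Φ(−2.57) = about 9%.
- *b* = 0.20 SD: 0.20/0.1635 = 1.22; Φ(−0.74) + Φ(−3.18) = about 23%.

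The non-central t distribution with 152 degrees of freedom gives 9.3% and 22.9% for the last two.

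**By assumed share and effect** (rejection rate):

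| Share *f* | *s* = 0 | *s* = 0.1 SD | *s* = 0.3 SD | *s* = 0.5 SD |
|---|---|---|---|---|
| 0.1 | 5.0% | 5.0% | 5.4% | 6.1% |
| 0.3 | 5.0% | 5.4% | 8.5% | 15.1% |
| 0.5 | 5.0% | 6.1% | 15.1% | 33.3% |
| 0.7 | 5.0% | 7.1% | 25.0% | 57.2% |

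The table runs from no consequence to a serious one, and the protocol does not say which cell applies. For scale, the difference detectable with 80% power is (1.96 + 0.84) × 0.1635 = about 0.46 SD, so the right-hand column assumes a colon effect larger than the study could reliably detect for splenectomy itself.

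**Precision of a restricted comparison.** If, for example, 32 controls remain, the standard error is √(1/90 + 1/32) = 0.206 SD. The restricted and full estimates share patients; by chance alone they differ with standard error √(1/32 − 1/64) = 0.125 SD. With half the controls removed, the expected gap between the two estimates equals *b*, so *b* = 0.10 SD is 0.8 standard errors and *b* = 0.20 SD is 1.6.

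**The case against.** A reader might infer that the comparator's metabolic values are in fact disturbed, or that the study's error rate is in fact inflated. The protocol supports neither. It gives no count of colon resections and no evidence that colon loss changes these outcomes, and it never calls the group metabolically unaffected; unexposed means only not splenectomised. Every rate above 5% comes from assumed inputs. This objection stands in full, and the point is put as a possible bias of unknown size and direction.

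Other objections:
- **Criterion 8 may be deliberately segment-specific**, for instance about absorption. That is possible, because the protocol gives no reason. It weakens the inference about purpose but does not alter who is eligible.
- **Criterion 9 already removes some colon resections.** Correct, and the share may be lower for it. It sets no length limit on those that remain.
- **A restricted comparison is too imprecise to settle the matter.** Partly right: a small shift would be lost in chance variation. It can still reveal a large dependence, and the site and length data are informative whatever the test shows.
- **Changing the main comparator now would be a post hoc choice**, since the protocol describes patients as already recruited. This stands, and the full group should remain the main comparator.
- **A sensitivity analysis may be in a statistical analysis plan that is not shown.** Its absence here is not the criticism. The criticism is of how the eligibility criterion is drawn.

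**Conclusion.** The point holds in limited form. As written, criterion 8 leaves non-malignant, non-irradiated colon resections of any length in the unexposed group, and the planned t-test cannot distinguish any effect of them from an effect of splenectomy. The consequence depends on two quantities the protocol does not give: the share of the 64 concerned and the effect of colon loss on each outcome. If either is zero, there is no bias and the error rate stays at 5%. A comparator shift of 0.10 SD would raise it to about 9%, and one of 0.20 SD to about 23%. These figures show how sensitive a 90 v 64 comparison is; they do not estimate what happened. The case for acting is that the study already holds the kind of record needed to examine the question cheaply.

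**What to change.** 1. From the surgical records already retrieved, extract the segment removed and its length for each of the 64 controls, and report both. Applying criterion 8 already required small-bowel length to be assessed.
2. Repeat each splenectomy v unexposed comparison using only controls with small-bowel resection of at most 10 cm and no colon resection. Give the difference with its 95% confidence interval beside the full-group result.
3. Keep the full unexposed group as the main comparator. Where the two estimates differ materially, qualify attribution to splenectomy. Judge the gap against its own chance variation (0.125 SD if 32 controls remain), not by whether significance is lost.

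Cost: two items from 64 records and one further run of the same comparisons. The downside is fewer controls and a wider interval in the restricted comparison: with 32 controls, a standard error of about 0.21 SD instead of 0.164 SD, so a normal-approximation 95% half-width of about 0.40 SD (1.96 × 0.206) instead of 0.32 SD (1.96 × 0.1635).

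### Exclusions for malignancy or radiotherapy history and for small-bowel resection over 10 cm apply only to the unexposed group; apply them to both groups and report how many splenectomy patients are affected

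*Protocol*

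**What the plan says.** The section Study protocol defines the cohort by operation: "Patients were divided into two groups: trauma splenectomy (exposed group) and bowel resection (unexposed group"). The comparator operation is "bowel resection due to bowel obstruction in our center between July 2008 and July 2013".

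Nine exclusions follow. Criterion 8 removes patients who had more than 10 cm of small bowel resected. Criterion 9 is "History of malignancy or radiotherapy". A closing parenthesis limits both: "criteria 8 and 9 were specific to unexposed group". Criteria 1 to 7 carry no such limit.

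On numbers, the section reports: "Of the 243 splenectomized patients, 90 patients who met our study criteria were willing to participate", and "Of 152 patients with bowel resection, 64 were willing to participate". Follow-up is given as "All patients were followed up for 5-10 years".

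The section Statistical analysis compares group means with Student's t-test at the 0.05 level and names no adjustment.

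**The concern.** Excluding controls with these conditions implies that the conditions could disturb the outcomes: lipid profile, HbA1c, fasting glucose, BMI and blood pressure. If so, the same reasoning applies to the exposed group. As written, a trauma patient with past cancer or radiotherapy, or one who lost the spleen and more than 10 cm of small bowel, may be counted as exposed. A control with the same history or resection may not.

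The two groups are then selected by different rules, and part of any difference in means could come from selection and not from the missing spleen. Adjusting for age or sex would not remove this, because the imbalance concerns the excluded conditions themselves. Since the rule is an explicit statement about eligibility, it is not a detail that a separate analysis plan would be expected to supply.

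**Working it through.** **Does another criterion close the gap?**

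- Criteria 1, 2, 3 and 5 act on lipids, glucose, blood pressure history and BMI at or before surgery. They catch a patient with prior cancer only if one of these was already abnormal.
- Criterion 4 concerns agents used during follow-up.
- Criterion 6 is open-ended, but is confined to diseases that may affect blood glucose.
- Criterion 7 concerns pancreatic damage.

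None of these reliably removes a splenectomy patient with a malignancy or radiotherapy history. None removes one with a concomitant small-bowel resection whose effect appears after the operation.

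**How large could the bias be?** The protocol gives no SD, effect size, power or count of affected patients, so there is no stated figure to reproduce and only a range can be shown.

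Inputs from the protocol: 90 exposed, 64 unexposed, significance level 0.05 (two-sided assumed).

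Assumed inputs: p, the share of the 90 with either condition, and d, the absolute mean shift of the outcome in those patients, in SD units.

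1. Standard error of the difference: sqrt(1/90 + 1/64) = sqrt(0.01111 + 0.01563) = 0.1635 SD.
2. Bias in the difference of means: p × d.
3. Bias in standard errors: s = p × d / 0.1635.
4. Two-sided type I error, normal approximation: 1 − Φ(1.96 − s) + Φ(−1.96 − s).

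| p | d (SD) | Bias (SD) | Bias (SE) | Type I error |
|---|---|---|---|---|
| 1% | 0.25 | 0.0025 | 0.015 | 0.050 |
| 1% | 1.0 | 0.01 | 0.061 | 0.050 |
| 5% | 0.25 | 0.0125 | 0.076 | 0.051 |
| 5% | 1.0 | 0.05 | 0.306 | 0.061 |
| 10% | 0.25 | 0.025 | 0.153 | 0.053 |
| 10% | 1.0 | 0.10 | 0.612 | 0.094 |
| 20% | 1.0 | 0.20 | 1.223 | 0.231 |

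**The same in clinical units, for illustration.** Assume a cholesterol SD of 40 mg/dL and a shift of 30 mg/dL, of either sign, in each affected patient.

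- SE = 40 × 0.1635 = 6.54 mg/dL.
- With 3 of 90 affected, the exposed mean moves by 3/90 × 30 = 1.0 mg/dL, or 1.0/6.54 = 0.15 SE.
- With 9 of 90 affected, it moves by 9/90 × 30 = 3.0 mg/dL, or 3.0/6.54 = 0.46 SE.
- The type I error is then about 0.053 to 0.075.

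**For scale.** With 90 and 64 patients, the difference detectable with 80% power is 0.1635 × (1.960 + 0.842) = 0.458 SD. A bias of 0.05 SD is about one ninth of that.

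**After the fix.** With the criteria applied to both groups, p is 0 in the exposed group and this source of bias disappears.

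**The case against.** The strongest defence concerns criterion 8. The comparator is itself a bowel operation, and a 10 cm limit keeps that surgery from becoming a metabolic exposure in its own right. The exposed group is defined by splenectomy, so a rule on extent of bowel resection has no natural counterpart there. This largely stands. What remains is the trauma patient who also lost more than 10 cm of small bowel. The protocol mentions no such patient, but its rules would admit one.

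A second defence is that malignancy may be linked to bowel obstruction in a way it is not linked to trauma, so the one-sided rule would remove an excess from the controls and make the groups more alike. That is plausible, though the protocol gives no frequencies. It explains why the rule was written, but not why an affected splenectomy patient should be exempt. If such patients are rare, a common rule costs almost nothing; if they are not, it is needed.

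A reader might infer more than the text supports:

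- **That affected splenectomy patients were in fact included.** The rules permit this, but no count shows it.
- **That the bias runs one way, towards a false lipid-lowering effect of splenectomy.** Nothing in the protocol gives bowel loss, cancer and radiotherapy a common sign across lipids, glucose and BMI. The bias could exaggerate a difference or mask one.
- **That a common rule would leave groups differing only by the spleen.** The controls would still have had obstruction and a bowel resection.

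**Conclusion.** The point holds as a one-sided eligibility rule that is explicit in the protocol, is not reliably covered by the other criteria, and is not corrected by the stated t-test. It is firm for criterion 9. For criterion 8 it applies only to splenectomy patients with a concomitant small-bowel resection.

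The consequence is a possible bias of unknown size and direction. On the assumed ranges it is negligible to small at a prevalence of 1 to 5%. It reaches a type I error of 0.094 at 10% prevalence with a 1 SD effect, and is serious (0.23) only at 20% with the same effect. The textual asymmetry is certain; actual distortion of the results is not shown. This is a cheap improvement and does not by itself undermine the comparison.

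**What to change.** Remove the clause limiting the two criteria to the unexposed group. Apply criterion 9 to both groups with the same time reference in each, since the criterion gives none. Apply criterion 8 also to splenectomy patients who had small bowel resected. Use the surgical records and histories already collected. Report how many of the 90 are removed under each criterion, and show the comparison with and without them.

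The cost is a re-check of 90 records and the loss of a few exposed patients. The loss of precision is slight: removing 3 gives sqrt(1/87 + 1/64) = 0.1647 SD, and removing 9 gives sqrt(1/81 + 1/64) = 0.1672 SD, against 0.1635 SD now. Even the larger loss widens the standard error by only about 2% (0.1672/0.1635 = 1.02).

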### Statistical analysis

After completion of data collection, data were entered in Excel and analyzed using SPSS software for Microsoft (version 22).

Student's t-test was used to compare the mean value of measured variables between the two groups. Chi-squared test was used to assess the relation between family history of diabetes mellitus (DM) and developing DM among participants. P value of  $< 0.05$  was considered significant.

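### The only stated comparison of splenectomy with bowel resection is an unadjusted t-test in a non-randomised cohort, which leaves age, sex, years since surgery and remaining baseline differences uncontrolled

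*Protocol*

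**What the plan says.** The Study protocol section describes a cohort at one centre, drawn from patients who had "trauma splenectomy or bowel resection due to bowel obstruction in our center between July 2008 and July 2013". Splenectomy patients are the exposed group (90 took part) and bowel resection patients the unexposed group (64 took part). Allocation was by operation, not by randomisation.

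The design gives partial control. Abnormal lipids or glucose at surgery, earlier hypertension, a BMI of 25 or more, and diseases that affect glucose are all excluded. Two further exclusions apply to one side only: "criteria 8 and 9 were specific to unexposed group". On follow-up it says "All patients were followed up for 5-10 years". On baseline information it says "Records of patients at the time of surgery were retrieved from hospital archive", without listing what the records contain.

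The Statistical analysis section gives one method for the group contrast: Student's "t-test was used to compare the mean value of measured variables between the two groups". The only other test is on a different question: "Chi-squared test was used to assess the relation between family history of diabetes mellitus (DM) and developing DM among participants". A P value below 0.05 "was considered significant". No covariate, matching, stratification or regression is mentioned in either section.

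**The concern.** A two-sample t-test estimates the effect of an exposure only if the groups are comparable in everything else that moves the outcome. Trauma patients and obstruction patients come to surgery by different routes, so nothing in the design makes them alike in age or sex. Blood pressure, lipids, glucose, HbA1c and BMI may all depend on age, sex and the years that have passed. The exclusions cut off the abnormal end of the baseline range but leave variation inside it.

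This comparison is the one that addresses the study's question. If the groups differ in age, for example, the t-test reports the age difference and any splenectomy difference as a single number. The bias could produce a difference where there is none or cancel one that exists, and the stated analysis gives the reader no means of telling which. Family history of diabetes is collected and treated as relevant to diabetes, yet it has no part in the group contrast.

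**Working it through.** The protocol states no sample-size calculation, effect size or SD, so there is no figure of its own to reproduce. What follows is an illustration for one confounder, age, in outcome SD units.

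**Inputs from the protocol:** 90 and 64 participants; significance level 0.05 (taken as two-sided, since the protocol does not say).

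**Assumed inputs:** age gap between groups g = 0.2, 0.5 or 1.0 SD; within-group age-outcome correlation r = 0.2 or 0.3; a true difference of 0.4 SD for the power example.

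**Step 1, precision.** SE = √(1/90 + 1/64) = 0.1635 SD, with 90 + 64 − 2 = 152 degrees of freedom.

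**Step 2, bias and false-positive rate when there is no true difference.** Bias = g × r. The rejection rate comes from the noncentral t distribution with noncentrality bias/SE.

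| g | r | Bias (SD) | Bias/SE | Rejection rate |
|---|---|---|---|---|
| 0.2 | 0.2 | 0.04 | 0.24 | 5.7% |
| 0.2 | 0.3 | 0.06 | 0.37 | 6.5% |
| 0.5 | 0.2 | 0.10 | 0.61 | 9.3% |
| 0.5 | 0.3 | 0.15 | 0.92 | 14.9% |
| 1.0 | 0.2 | 0.20 | 1.22 | 22.9% |
| 1.0 | 0.3 | 0.30 | 1.83 | 44.6% |

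**Step 3, masking.** With a true difference of 0.4 SD and no bias, power is 68.1% (0.4/0.1635 = 2.45). A bias in the opposite direction of 0.04, 0.1, 0.2 or 0.3 SD leaves net differences of 0.36, 0.3, 0.2 and 0.1 SD. Power then falls to 59.0%, 44.6%, 22.9% and 9.3%.

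**Step 4, price of the age term alone.** The SE is multiplied by √[(1 − r²)(1 + p(1 − p)g²)], with p = 90/154 and p(1 − p) = 0.243. For r = 0.2 and 0.3 respectively:
- g = 0.2: 0.98 and 0.96
- g = 0.5: 1.01 and 0.98
- g = 1.0: 1.09 and 1.06

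**Step 5, simulation of the fuller model.** The same six scenarios were simulated with no true group effect and 4,000 replicates each. Sex, years since surgery and family history were balanced and unrelated to outcome. The unadjusted test rejected in 5.5% to 44.9% of replicates. Regression on group, age, sex, years since surgery and family history, with HC3 robust standard errors, rejected in 4.1% to 5.0%. Its mean SE was 0.99 to 1.13 times the unadjusted one.

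**Step 6, degrees of freedom.** With a baseline term added, the model has six terms and an intercept, so 154 − 7 = 147 degrees of freedom remain. The critical t is 1.976, the same to three decimals as at 152.

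**The case against.** The strongest reply is that this is a risk and not a demonstrated bias. Nothing in the protocol shows that the groups differ in age, sex or years since surgery, and they may happen to be balanced. Both come from one centre and one surgery window, and the exclusions cover the baseline counterparts of most measured outcomes. At an age gap of 0.2 SD the inflation is trivial, and the 45% figure needs a gap of a full SD. A separate analysis plan may add covariates. All of this is fair as to size. It does not rescue the method, because the protocol does not leave the group comparison open: it names an unadjusted test, and balance that is neither designed nor shown cannot be assumed.

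Other points stand as limits:
- The illustration covers age only. No figure is offered for sex, years since surgery or baseline level.
- Years since surgery is the weaker candidate, since both groups share the window and no reason is given for it to differ.
- The simulation shows recovery only for a confounder that is measured and linear.
- The simulated model had no baseline term, and its 13% ceiling depends on the other covariates being balanced. With an assumed sex split of 80% v 50%, an age gap of 1 SD and r = 0.2, the SE ratio was 1.18.
- The bowel-length exclusion belongs naturally to the comparator operation. The exclusion for malignancy or radiotherapy is the more meaningful asymmetry, and the covariates proposed here do not correct it.

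**Conclusion.** The concern holds and should be fixed. The one stated comparison of exposed and unexposed patients does not fit a non-randomised cohort of two different surgical populations. That conclusion rests on the text alone. The error rates (5.7% to 45% in place of 5%, and power down from 68% to as little as 9%) show only what plausible imbalance could do with 90 and 64 patients. They depend on assumed age gaps, correlations and a true difference that the protocol does not supply. The actual size and direction of any bias cannot be determined from it.

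**What to change.** For each measured outcome, make the main analysis a linear regression on group, age, sex, years since surgery, family history of diabetes and, where the surgery-time records hold it, the baseline value of the same variable. Use heteroscedasticity-robust standard errors and report the adjusted difference with its 95% confidence interval. Where no baseline value was recorded, omit that term only. State in advance whether this is decided per outcome or per patient, so that patients are not dropped silently.

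Tabulate age, sex, years since surgery and available baseline values by group. Keep the unadjusted comparison as descriptive. State that unmeasured differences between trauma and obstruction patients remain, so the adjusted difference is an association. The change concerns the continuous outcomes that the t-test covers; the protocol states no group comparison for developing diabetes.

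The cost is a change of wording and one regression per outcome in the software already named, with no new patients. Family history is already collected. That age, sex, operation date and numeric baseline values are in the records, or can be obtained at the history-taking visit, is an assumption. The SE may widen: by up to about 13% in the main scenarios, and by 18% when sex was also assumed to be imbalanced.

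### Student's pooled t-test is the only test named for continuous group comparisons; at 90 v 64 patients, Welch's test would protect against unequal SDs at no cost

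*Protocol*

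**What the plan says.** The Statistical analysis section of the Protocol states that Student's "t-test was used to compare the mean value of measured variables between the two groups". It names no unequal-variance version, transformation or rank test. The only other test is for a binary outcome: "Chi-squared test was used to assess the relation between family history of diabetes mellitus (DM) and developing DM among participants". Significance is set at P below 0.05, with no sidedness given.

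The Study protocol section gives the group sizes. For the exposed group: "Of the 243 splenectomized patients, 90 patients who met our study criteria were willing to participate". For the unexposed group: "Of 152 patients with bowel resection, 64 were willing to participate". The blood measurements come from "drawing blood samples for measurement of lipid profile, Hb A1C and fasting blood sugar"; blood pressure and BMI are also assessed. One exclusion is "Disturbed blood glucose levels at the time of surgery", which applies to the state at surgery. Patients are then followed for 5-10 years, and those who develop diabetes in that time are part of the analysis.

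The Protocol reports no SD, distribution or variance ratio for any variable, and no power calculation.

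**The concern.** Student's t-test estimates one common variance and uses it for both groups. When group sizes differ, that estimate leans towards the larger group. If the SDs also differ, the standard error is wrong: too small when the smaller group is the more variable, too large when the larger group is.

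There are two reasons to expect unequal SDs here. The groups come from different surgical populations, trauma and bowel obstruction. Also, the design starts everyone with undisturbed glucose and lets diabetes emerge. If diabetes becomes commoner after splenectomy, the exposed group gains a right tail in fasting sugar and HbA1c, so its mean and SD rise together. The exposed group is the larger one, so the pooled test would be weakened in the situation the study is meant to detect.

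**Working it through.** The Protocol has no figure of its own to reproduce on this point.

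**Inputs from the Protocol:** n₁ = 90 (splenectomy), n₂ = 64 (bowel resection), α = 0.05. **Assumed:** a two-sided test, the SD ratios, and the diabetes scenarios below.

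**1. Size of the pooled test, by formula.**

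- Pooled variance: s² = (89·σ₁² + 63·σ₂²)/152
- Variance of the difference that the test believes: s²·(1/90 + 1/64) = s² × 0.026736
- True variance of the difference: σ₁²/90 + σ₂²/64
- Actual size ≈ 2·[1 − Φ(1.976 × √(believed/true))], where 1.976 is the t critical value on 152 degrees of freedom

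Worked case, σ₁ = 1 and σ₂ = 1.5: s² = (89 + 141.75)/152 = 1.518. Believed variance = 0.04059. True variance = 0.01111 + 0.03516 = 0.04627. The ratio is 0.877 and its root 0.937, so the size is 2·[1 − Φ(1.850)] = 6.4%.

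**2. The same by simulation** (normal data, equal means, 40,000 to 100,000 null studies per case; ranges are across repeat runs).

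| SD, group of 90 : group of 64 | Formula | Student, simulated | Welch, simulated |
|---|---|---|---|
| 1 : 1 | 4.8% | 4.9-5.1% | 5.0% |
| 1 : 1.5 | 6.4% | 6.5-6.6% | 4.9-5.1% |
| 1 : 2 | 7.5% | 7.7-7.8% | 5.0-5.1% |
| 1.5 : 1 | 3.5% | 3.6-3.7% | 4.9-5.0% |
| 2 : 1 | 2.9% | 2.9-3.2% | 4.9-5.1% |

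At the milder ratios of 0.8 and 1.25 (group of 90 over group of 64), Student's size is 5.8% and 4.0%.

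**3. Skew alone.** With the same lognormal distribution in both groups and log-SD from 0.2 to 0.8, Student's size is 4.7-5.0%.

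**4. Power when diabetes is commoner in the exposed group.** Assumed fasting sugar: mean 92, SD 9 without diabetes; mean 150, SD 30 with it. At diabetes proportion p, the group mean is 92 + 58p and the variance is 81(1−p) + 900p + 58²·p(1−p). At p = 15% the variance is 68.85 + 135 + 428.91 = 632.76, so the SD is 25.2. At p = 5% it is 76.95 + 45 + 159.79 = 281.74, so the SD is 16.8. The SD ratio is 1.50. Simulated power:

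| Diabetes, exposed v unexposed | SD ratio | Student, raw | Welch, raw | Loss with Student | Welch, log scale |
|---|---|---|---|---|---|
| 15% v 5% | 1.50 | 35.3% | 41.7% | 6.4 points | 38.0% |
| 15% v 3% | 1.76 | 52.5% | 59.9% | 7.4 points | 54.3% |
| 20% v 5% | 1.67 | 62.4% | 68.0% | 5.6 points | 64.5% |

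The log scale does worse than raw Welch in all three cases.

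**5. Power for a purely lognormal variable.** With a multiplicative shift set to give about 80% power on the log scale, raw Student's t loses about 1 point at log-SD 0.2, 4-6 points at 0.5 and 11-14 points at 0.8. The gain from logs therefore depends on marked skew and a multiplicative effect.

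**The case against.** The strongest reply is that the Protocol does not write that variances are assumed equal. Pooling is inferred from the test's name. SPSS, the named software, prints the unequal-variance result beside the pooled one, and the text does not say which is read. Variance form and distribution checks are also often left to an analysis plan, which is not shown here. This limits the weight of the point but does not remove it: the document names a specific test, that name ordinarily means the pooled version, and a better choice can be stated at no cost.

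Several stronger readings are tempting and are not supported:

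- *That P values are wrong because the groups are unequal in size or the outcomes skewed.* At 90 v 64 with equal SDs the size is about 5%, and with skew alone 4.7-5.0%. Unequal SDs are needed.
- *That the true false-positive rate is known not to be 5%.* No SDs are given, so the departure is conditional. At SD ratios between 0.8 and 1.25 it is 4.0-5.8%.
- *That glucose and triglycerides are skewed.* The Protocol shows no distributions and does not name triglycerides apart from the lipid profile. A right tail in glucose is plausible but unquantified.
- *That the t-test covers every outcome.* The analysis of family history against diabetes uses chi-squared.
- *That fasting sugar should be log-transformed.* Under the diabetes mechanism this lowers power relative to raw Welch, and it changes the target from the stated comparison of means to a ratio of geometric means.

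**Conclusion.** The point holds as a minor one. The pooled t-test is a weaker choice than Welch's test for this layout. If the SDs differ by a factor of 1.5-2, the nominal 5% error becomes about 6.5-8% when the group of 64 is the more variable and about 3-4% when the group of 90 is; Welch's test stays at 4.9-5.1%. If diabetes is commoner in the exposed group at the assumed rates, the pooled test gives up about 6-7 points of power.

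The two results answer different questions. The size figures apply to a variable whose means are equal while its SDs differ. The power figures apply when new diabetes moves both. All of them rest on assumed SD ratios, diabetes rates and glucose values, because the Protocol gives none.

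**What to change.** In the Statistical analysis section, replace Student's t-test with Welch's unequal-variance t-test for all between-group comparisons of means, and report each mean difference with its 95% confidence interval. The chi-squared analysis is unaffected.

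Do not make a log transform mandatory. A log-scale analysis of lipids that are clearly lognormal may be added as a sensitivity analysis, reported as ratios and labelled as such.

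The cost is a change of wording: no new data are needed, SPSS already prints the unequal-variance result, and when the SDs are equal Welch's test holds the same 5% error, with power that is practically unchanged (79.5% v 79.6%).
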